## **8.0 Genetic Analysis Information**

8.1 N/A

## **9.0 Sharing of Results with Subjects**

9.1 N/A

## **10.0 Study Timelines**

10.1 The duration of participation of patients that enroll in the study will be from time of enrollment to discharge or transfer from CMH

10.2 The study timeline is as follows:

Stage 1, patient accrual - 10/1/2018 – 12/31/2020

Stage 2, data analysis - 1/1/2021 - 3/31/2021

Stage 3, grant applications- 3/1/2021

Projected start date is upon IRB approval. Projected start date 10/1/2018

Total length of time: 3 years

## **11.0 Inclusion and Exclusion Criteria**

### Inclusion Criteria

- Neonates born prior to or at 32 weeks gestation admitted to NICU at CMH

### Exclusion Criteria

- Infants with chromosomal or multiple congenital anomalies
- Unable to ultrasound the bowel (e.g. gut in silo, omphalocele, gastroschisis)
- Infants who are greater than 36 corrected weeks upon admission
- Infants who have had recent abdominal surgery
- Infants who have had a previous bowel perforation

## **12.0 Vulnerable Populations**

12.1 This study involves no greater than minimal risk to the subjects enrolled. BUS is a noninvasive imaging tool used in standard of care procedures often for premature infants in the NICU currently. Fecal calprotectin sampling is also noninvasive and would only involve a stool sample obtained from a diaper. Consent will be obtained from the patients LAR after a full explanation of the study is given and any questions the LAR has are answered. Assent will not be obtained due to age.

## **13.0 Local Number of Subjects**

13.1 This pilot study will enroll 80 NICU patients per year, aiming to randomize 40 patients a year with suspected NEC.

## **14.0 Screening and Recruitment Methods**

14.1 Potential subjects will be screened and recruited in the NICU at Children's Mercy Hospital upon admit. Screening will be done by a

CMH NICU fellow or research coordinator on the study and consent will be obtained shortly after eligibility is confirmed.

- 14.2 The source of subjects will solely come from the CMH NICU.
- 14.3 Potential subjects will be identified by the NICU staff and a member of the study team will be notified to confirm eligibility and approach the subject and LAR to obtain consent if desired.
- 14.4 A pre-screening log will be maintained for the purpose of tracking enrollment. This will include DOB, MRN, eligibility, and choice to participate. This will ensure a patient is not approached more than once.

## **15.0 Reimbursement, Payment and Tangible Property provided to subjects**

- 15.1 N/A

## **16.0 Withdrawal of Subjects**

- 16.1 A subject may be withdrawn without their consent if they undergo any medical procedure during the course of their admission that excludes them from safely undergoing a BUS.
- 16.2 Subjects may choose to discontinue study participation at any time, for any reason, specified or unspecified, and without prejudice. Subjects may be discontinued from the study for any of the following reasons:
  - At the subject's or their parent's/LAR's request
  - At the discretion of the site investigator as deemed appropriate for any reason

Procedures for orderly termination will include a discussion with the parents or LAR for the reasons behind early termination.

- 16.3 If a subject withdraws from the research study, data that has already been collected may still be used; however, no new information will be collected except information related to adverse events or other safety issues.

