## 4.0 Study Endpoints

4.1 The primary endpoint for this study will be feasibility of recruitment into a diagnostic RCT and implementation of BUS intervention in infants with suspected NEC. Feasibility parameters to be assessed include recruitment, randomization, retention, and crossover. Recruitment will be measured as proportion of eligible infants who are enrolled, while randomization will be proportion of enrolled infants who develop NEC suspicion and undergo randomization. Retention will be defined as proportion of infants who complete the study. Crossover will be measured by proportion of infants randomized to standard of care who crossover to BUS arm. Successful implementation of intervention will be assessed by (1) proportion of properly completed BUS studies by sonographers; (2) proportion of adherence to standardized reporting template by radiologists, and (3) timeliness of stool collection in proximity to the BUS. For the secondary endpoint measures, time to achieve full enteral feeds will be defined as days to reach enteral feeds of 120mL/kg/day following suspension of feeds due to suspected NEC; and total antimicrobial days will be defined as days treated with empiric antibiotics due to suspected NEC. For the exploratory aim, the primary endpoint will be changes in serial fecal calprotectin levels and its association with NEC diagnosis.

[figure not shown]

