BUS performance and interpretation. US performance and interpretation will be performed by a sonographer and radiologist, respectively, as per standard clinical work-flow. All BUS results will be available to the study team (i.e. no blinding). Variability in performance of US by sonographers will be minimized by pre-study training and quick reference cards in each US machine as detailed above. Likewise, variability in US interpretation will be minimized by the pre-study training as well as the use of a standardized template for reporting US results (see **Appendix**). All study US exams will be over-read by the study radiologists to ensure accurate interpretation. In cases of differences in their readings, final interpretation will be made by the study radiologists and these results will be communicated to the clinical team.

Fecal calprotectin measurement. Stool will be collected from a diaper following study enrollment regardless of rate of feeds. We will do an additional collection of stool after five weeks of life to get a baseline calprotectin level. "Baseline" is defined as an infant who is greater than or equal to five weeks of age and is tolerating full enteral feeds of at least 120 mL/kg/day. All stool samples will be collected by the NICU nurse or study staff. Stools can be stored for up to 72 hours if needed and then processed using the Fecal Calprotection High Range Quantitative Quantum Blue assay. All results will be recorded in Redcap. If a baby develops a concern for NEC, the next three stool samples at least a day apart will be collected for FC analyzation. An additional stool sample will also be collected at the resolution of NEC watch, which is defined by tolerance of  $\geq 120$ mL/kg/day of enteral feeds for at least two days. Infants who have repeated concern for NEC will again have the first three stool samples collected with each event, with another stool also collected at resolution of NEC. The stool samples will be kept suspended in a buffer in a test tube for the duration of the study in the event a sample needs to be retested.

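### Section 16.1 may take an infant out of the whole study when a procedure rules out safe bowel ultrasound, and nothing provides for following that infant further

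*Combined protocol and SAP*

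**What the plan says.** Section 16.0 gives three ways out of the study and one rule on data.

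- **16.1** lets the study withdraw a subject without consent "if they undergo any medical procedure during the course of their admission that excludes them from safely undergoing a BUS". The verb is permissive, no procedure is named, and neither arm is exempted.
- **16.2** covers families: "Subjects may choose to discontinue study participation at any time". It also lets the site investigator discontinue a subject for any reason thought appropriate.
- **16.3** is the only rule on data after withdrawal. What exists is kept ("data that has already been collected may still be used"), but "no new information will be collected except information related to adverse events or other safety issues".

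The outcomes that bear on this are in sections 4.0 and 6.0. Retention is one of the primary feasibility parameters: "Retention will be defined as proportion of infants who complete the study". The secondary measures are time to full feeds, counted as "days to reach enteral feeds of 120mL/kg/day following suspension of feeds due to suspected NEC", and antimicrobial use, where "total antimicrobial days will be defined as days treated with empiric antibiotics due to suspected NEC". For calprotectin, section 6.0 plans three stools after each concern for NEC and then a later one: "An additional stool sample will also be collected at the resolution of NEC watch". Section 6.1 keeps infants with repeat episodes in their assigned arm and ends participation at discharge or transfer. It schedules BUS only in the AXR-plus-BUS arm.

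**The concern.** The reason given in 16.1 is the safety of one imaging test, but the action is removal from the study. Reading the chart and taking stool from a diaper do not depend on that test. The AXR-only arm shows that infants can be followed in this trial without BUS. Yet 16.1 covers that arm too, so a control infant could be withdrawn for being unable to have a test that the protocol does not schedule for that infant.

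Two things are at stake. First, retention could fall although no family left and chart follow-up was still possible, and a reader of the pilot could not tell the two kinds of loss apart. Second, outcomes that occur after the procedure could be missing. If the procedures that preclude BUS tend to occur in sicker infants, that missingness would be informative. Section 20.1 intends the pilot data to support the power analysis of the larger study.

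**Working it through.** **Step 1. What 16.1 stops.** Its object is the subject, not the ultrasound. No section describes an infant who stops study BUS under 16.1 and continues in follow-up.

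**Step 2. Whether 16.3 then applies.** 16.3 is conditional on a subject withdrawing. 16.1 speaks of a subject being withdrawn, and 16.2 separates those who choose to leave from those whom the study discontinues. Applying 16.3 to a 16.1 withdrawal is the natural reading, because there is no other post-withdrawal rule, but the text does not say so. If 16.3 does not apply, no section says what is collected from such an infant.

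**Step 3. Which outcomes are exposed.** If an infant is withdrawn under 16.1 and 16.3 applies:

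| Item | Effect |
|---|---|
| Data before the procedure; safety data | Kept |
| Time to full feeds | Lost if not yet reached |
| Antimicrobial days | Truncated if treatment for suspected NEC continues |
| Resolution stool, repeat-event stools | Lost if still due |
| Later NEC episodes | Lost |
| Aims 1(a) and 1(b), surgery and days to surgery | Largely kept: an operation that is itself the trigger, and its date, come before withdrawal |
| Aim 1(c), days NPO | Largely unaffected by a surgical trigger: limited to medically managed infants |

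**Step 4. Retention per withdrawal.** The plan's own totals reproduce (sections 1.0, 13.1, 20.2 and 20.3):

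- 100 approached × 0.80 consenting × 0.50 with NEC suspicion = 40 randomized per year
- 40 × 2 years = 80 randomized
- 80 enrolled per year × 2 years = 160 enrolled

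This arithmetic has no term for withdrawal. With N infants in the denominator, k withdrawn under 16.1, no other loss, and withdrawal counted as not completing:

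Retention = (N − k)/N, so each withdrawal costs 1/N.

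- N = 80: 1/80 = 1.25 percentage points
- N = 160: 1/160 = 0.625, or 0.63 percentage points

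Both are shown because section 4.1 does not say whether the denominator is enrolled or randomized infants.

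**Step 5. Illustration.** The documents give no rate of 16.1 withdrawals, so every k below is an assumption (4, 8 and 16 are 5%, 10% and 20% of 80).

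| k (assumed) | Retention, N = 80 | Retention, N = 160 |
|---|---|---|
| 1 | 79/80 = 98.75% | 159/160 = 99.38% |
| 4 | 76/80 = 95% | 156/160 = 97.5% |
| 8 | 72/80 = 90% | 152/160 = 95% |
| 16 | 64/80 = 80% | 144/160 = 90% |

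In the N = 80 column k counts randomized infants only. In the N = 160 column it counts any enrolled infant, because 16.1 is not limited to those randomized.

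**The case against.** The strongest reply is that nothing here is compulsory. The investigator may already keep an infant who cannot have BUS, no section makes continued BUS a condition of participation, and AXR-only infants are followed without it by design. This stands. A reader might infer that the plan forbids follow-up without BUS. It does not: what is missing is a provision for infants who have been withdrawn under 16.1.

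Second, the harm needs a chain of events: a triggering procedure, a decision to withdraw, 16.3 taken to apply, and an outcome still to come. This also stands, and it is why the point is conditional.

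Third, a reader might infer that surgery is the trigger, so that surgical infants are dropped and the surgical comparison is biased. The documents do not support this. Section 11.0 excludes infants with a recent abdominal operation, but lists that separately from bowel that cannot be scanned, and 16.1 names no procedure. Surgery is plausible, not stated, and step 3 shows that the surgical aims would be largely intact even then.

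Fourth, in a pilot of BUS delivery, an infant who can no longer have BUS is arguably a real feasibility result. That is fair, but it is a result about the intervention. It is better reported as a BUS omission than merged into loss to follow-up.

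Finally, 16.2 would still allow discretionary discontinuation if 16.1 were reworded. That is correct, and the fix has to cover reporting of those exits as well.

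**Conclusion.** The point holds in a limited form. 16.1 allows, without requiring, removal from the whole study for a reason that concerns only the ultrasound. For infants so removed, follow-up is not provided for and later non-safety data would probably stop. The size that rests on the documents' own totals is 1.25 points of retention per withdrawal with 80 randomized, or 0.63 with 160 enrolled, provided that withdrawal counts as not completing, which section 4.1 leaves undefined. Everything beyond that depends on assumed counts.

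Three further inferences go too far. No retention threshold is stated, so no go/no-go decision can be shown to change. Uneven use between arms is possible, because BUS is scheduled in one arm, results are unblinded and withdrawal is discretionary, but neither its size nor its direction can be derived. And section 20.1 does not say which outcome will feed the later power analysis, so damage to that calculation is not shown.

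Severity is minor to moderate. The change is worth making because it is cheap and removes an avoidable source of possibly informative missing data.

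**What to change.** 1. Reword 16.1 so that inability to have BUS safely ends study BUS only and is not by itself a reason for withdrawal from the study. The clinical judgement that BUS is unsafe stays as it is.
2. State that such an infant, if randomized, remains in the assigned arm, and that in both arms chart outcomes and the planned stools are collected to discharge or transfer unless the parent or legally authorized representative asks to stop.
3. State that the stop on data collection in 16.3 does not apply to these infants. Leave 16.3 unchanged for other withdrawals.
4. In section 4.1, count follow-up to discharge or transfer as completion, and name the denominator for retention.
5. Report BUS omissions and withdrawals, including discretionary ones under 16.2, by arm and reason.

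The cost is a minor protocol amendment and some extra chart abstraction. No new procedure is needed, since the stools are already planned. The consent form was not available for this review. It should be checked for permission to continue collection, and amended if that is lacking.

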## **17.0 Risks to Subjects**

- 17.1 This study involves no greater than minimal risk to the subjects enrolled. BUS is a noninvasive imaging tool used in standard of care procedures often for premature infants in the NICU currently. Fecal calprotectin sampling is also noninvasive and would only involve a stool sample obtained from a diaper.

## **18.0 Potential Benefits to Subjects**

18.1 There may be no direct benefit to the patient in the study, however, imaging done as part of the study will be available to any treating physician and may be helpful in medical management of the patient. Any procedures or treatments performed as a result from the imaging will be the financial responsibility of the patient.

## 19.0 Investigator Assessment of Risk/Benefits Ratio: (IRB makes the final determination)

Select as applicable:	Pediatric Risk Category:	
X	Category 1	Research not involving greater than minimal risk (45 CFR §46.404 and 21 CFR §50.51)
	Category 2	Research involving greater than minimal risk but presenting the prospect of direct benefit to the individual subjects. (45 CFR §46.405 and 21 CFR §50.52)
	Category 3	Research involving greater than minimal risk and no prospect of direct benefit to individual subjects, but likely to yield generalizable knowledge about the subject's disorder or condition. (45 CFR §46.406 and 21 CFR §50.53)
	Category 4	Research not otherwise approvable which presents an opportunity to understand, prevent, or alleviate a serious problem affecting the health or welfare of children. (45 CFR §46.407 and 21 CFR §50.54)
Select if applicable:	Adult Risk Category:	
	Not Greater than Minimal Risk	
	Greater than Minimal Risk	

## 20.0 Data Management and Confidentiality

20.1 This is a pilot study only to evaluate feasibility of a larger clinical trial. We will use the pilot data in the future to perform a power analysis for the larger study.

20.2 We anticipate having to approach ~100 patients/year to achieve the 40 patients/year needed for our pilot study. We are assuming a NEC suspicion incidence rate of 50% and approximately 20% of parents/patients declining to consent for the study (e.g. 100 patients \* 80% consent rate \* 50% with NEC suspicion = 40 patients/year).

20.3 With a target of 80 patients randomized, we anticipate the enrollment period to last ~2 years. We will stop consenting patients as soon as we meet our desired enrollment.

20.4 A certificate of confidentiality will not be sought for this study.

20.5 Study data will be evaluated by the PI throughout the duration of the study for QA.

20.6 Patient information will be maintained in a REDCap application and will be housed within the CMH Data Center by the Division of Biomedical Informatics. The hosting server has an internal failover two-node cluster. The CMH Data Center is constantly staffed by qualified personnel and physical access is limited to authorized personnel. The

Center has optimized conditions for the servers and stabilized electrical supply. The database has a full backup. The database server is located inside the CMH corporate firewall. A person must have CMH system access to login. Additional security for the study patient database restricts access to only those persons specifically granted authorization by the Principle Investigator. It is possible for data to be downloaded from REDCap. Individuals who lack authority to see confidential data can download reports with non-identifiable data only. The core research group will have the ability to download sensitive fields and if such a download occurs, REDCap maintains a record of who, what, when, and to where copies of the database were imported.

## **21.0 Provisions to Monitor the Data to Ensure the Safety of Subjects**

N/A

## **22.0 Provisions to Protect the Privacy Interests of Subjects**

- 22.1 Privacy interests for subjects will be maintained by limiting interaction with subjects and LAR to only study personnel at the discretion of the treating physician.
- 22.2 This study is voluntary, the physicians involved do not have any financial gain or interest with the study. Subjects may withdraw participation at any time and their care and treatment at CMH will not be compromised. Subjects and their families will be told that their participation is voluntary and that they may stop at any time.
- 22.3 Only IRB approved members of the study team will be granted access to the study folder located on the network drive or the REDCap database. Additionally, study team members who are responsible for collected data only will be granted limited access to REDCap, allowing them to record data only.
- 22.4 PHI to be accessed and/or recorded for this research study includes: DOB, MRN, dates of service (BUS exams, FC results, HSCT, lab dates and dates of severity milestones and death if applicable) will be recorded.
- 22.5 HIPAA authorization will be wrapped into permission/assent/consent form.

## **23.0 Compensation for Research-Related Injury**

- 23.1 There is no more than minimal risk to subjects.

## **24.0 Economic Burden to Subjects**

- 24.1 There will be no cost to patients for participating in this study. All BUS imaging and Fecal Calprotectin tests will be covered by study funds. However, patients will be charged for any standard of

care imaging, procedures, or treatments that coincide with their diagnosis (i.e. AXR, antibiotics, surgery).

## 25.0 Permission/Accent/Consent Process

25.1 Permission/Accent/Consent will be obtained by a LAR from all patients wishing to participate.

- The p/a/c process will take place in the CMH NICU at the patient's bedside.
- The patient's LAR will be given time to review materials and ask any questions.
- We will be following CMH research policies on informed consent.
- We will have the option to obtain consent via telephone in the event a parent or guardian is unavailable at the bedside or only comes on weekends.
- We will follow CMH policy 10.05 Telephone and Telemedicine Consent Process.
- Parental permission will be obtained from one parent or LAR.
- This study will only occur in Missouri at the Children's Mercy Hospital – Adele Hall.
- Other than biological parents, LARs such as an adoptive parent will be allowed to consent for a child's participation in this study.

*Consent at 18 years of age, when minor subjects become adults*

N/A

*Waiver or Alteration of Parental Permission or Child Assent Process (permission and/or assent will not be obtained, required information will not be disclosed, or the research involves deception)*

N/A

*Waiver or Alteration of Consent Process (consent will not be obtained, required information will not be disclosed, or the research involves deception)*

N/A

*Non-English Speaking Subjects*

- P/A/C forms will be translated into Spanish by ORI Translations program.

**Cognitively Impaired Adults**

N/A

**Adults Unable to Consent**

N/A

**26.0 Process to Document Permission/Accent/Consent**

- 26.1 Study staff will be following [CM Research Policy 10.04 Obtaining Permission/Accent/Consent](#).
- 26.2 We request a waiver of documentation of P/A/C for patients in which phone consent was obtained since the study involves no more than minimal harm.

**27.0 Setting**

- 27.1 Potential subjects will be recruited from the NICU at CMH Adele Hall. NICU staff may notify study team members of an eligible patient and eligibility will be confirmed upon screening. Once eligibility is confirmed, the subject will be approached for consent. All procedures (BUS, AXR, and fecal calprotectin testing) will take place at the patient's bedside in the CMH NICU.

**28.0 Resources Available**

- 28.1 The facilities and other resources available to the research team include everything needed to undertake and complete the proposed pilot study successfully. The NICU at CMH provides clinical care to over 150 preterm infants  $\leq$  28 weeks gestation per year and thus provide access to sufficient patients. The culture of clinical research is vibrant in the NICU with high recruitment rates for current studies. US services at CMH are also robust. CMH has in-house sonographers to perform US and radiologists to interpret these studies 24/7. Each member of the collaborative team has strong commitment from their departments for this study in the form of (1) protected research time, (2) cost sharing of salaries, (3) administrative support, and (3) research coordinator effort. In summary, the outstanding facilities, strong intellectual environment, and abundant resources available to the team are strongly supportive of the proposed research and overall success of the project.

There are 20 sonographers which are all registered diagnostic medical sonographers (RDMS). 18 of the sonographers have also passed their pediatric sonography boards.

All imaging will be performed portable in NICU by standard portable radiography (GE) and ultrasound equipment (GE Logiq E9 and Zonare Z-One Smartcarts) already in practice at our institution.

Fecal calprotectin tests will be performed on Quantum Blue Reader testing devices that utilize Fecal Calprotectin fCAL high range tests and CAKEX Cap Devices to obtain calprotectin levels.

[name], one of the Co-Investigators, will present the proposed study at a CMH NICU Conference held monthly to ensure all NICU physicians are aware of the upcoming process and logistics of the study.

